11.3.2 Statistical Methods

Analysis of Quantitative Laboratory Parameters (Hematology and Chemistry)

Though the protocol indicates utilizing the Rheumatology Common Toxicity Criteria (RCTC) scale for grading laboratory values, given that the National Cancer Institute Common Toxicity Criteria for Adverse Events (NCI CTCAE) scale includes a more comprehensive list of laboratory values; the lab analyses based on the NCI CTCAE scale will be presented. Changes from Baseline to each scheduled visit and to the final value in continuous laboratory parameters will be summarized with the mean, standard deviation and median. The Baseline and visit/final value means will also be presented for subjects who have both the Baseline and visit/final values (see Section [6.0](#) for the definition of Baseline and final values).

If there are multiple post-baseline measurements on the same day, average value will be used.

Shift Tables

Shift tables for changes from Baseline according to the normal range will be provided for each hematology, and clinical chemistry parameter. Shifts from Baseline to the following endpoints will be considered: minimum value, maximum value and final value. Categories of "low or normal" and "high or normal" will be included at Baseline in addition to the categories of "low," "normal," "high" and "missing."

If there are multiple post-baseline measurements on the same day, the last value will be used.

Potentially Clinically Important Laboratory Values

Frequencies and percentages of subjects with post Baseline lab values meeting the following criteria in [Table 25](#) and [Table 26](#) will be summarized. Of note, a post baseline value must be more extreme than the baseline value to be considered a potentially clinically important finding.

Table 25. Criteria for Potentially Clinically Important Chemistry Values

Chemistry Variables	Units	Definition of Potentially Clinically Important Current (Version 4) NCI CTCAE Grade 3 or Greater	
		Very Low	Very High
TBL	mcmol/L		> 3.0 × ULN
SGOT/AST	U/L		> 5.0 × ULN
SGPT/ALT	U/L		> 5.0 × ULN
Albumin	g/L	< 20	
Glucose	mmol/L	< 2.2	> 13.9
Triglycerides	mmol/L		> 5.7
Creatinine	mcmol/L		> 3.0 × ULN
Sodium	mmol/L	< 130	> 155
Potassium	mmol/L	< 3.0	> 6.0
Calcium	mmol/L	< 1.75	> 3.1
CPK	U/L		> 5.0 × ULN
Total Cholesterol	mmol/L		> 10.34
GGT			> 5.0 × ULN
ALP			> 5.0 × ULN

Note: A post baseline value must be more extreme than the baseline value to be considered a potentially clinically important finding.

Table 26. Criteria for Potentially Clinically Important Hematology Values

Hematology Variables	Units	Definition of Potentially Clinically Important Current (Version 4) Grade 3 or Greater	
		Very Low	
Hemoglobin	g/dL	< 8.0	
Platelets count	10 ⁹ /L	< 50.0	
WBC count	10 ⁹ /L	< 2.0	
Neutrophils	10 ⁹ /L	< 1.0	
Lymphocytes	10 ⁹ /L	< 0.5	

Note: A post baseline value must be more extreme than the baseline value to be considered a potentially clinically important finding.

A separate listing will be provided that presents all of the subjects and values that are NCI CTCAE toxicity grade 3 or above. For each of these subjects, the whole course of the respective parameter will be listed. The NCI CTCAE grading is shown in [Table 27](#) below:

Table 27. NCI CTCAE Grading

Test	Grade 1	Grade 2	Grade 3	Grade 4
SGPT/ALT increased	> ULN – 3.0 × ULN	> 3.0 – 5.0 × ULN	> 5.0 – 20.0 × ULN	> 20.0 × ULN
SGOT/AST increased	> ULN – 3.0 × ULN	> 3.0 – 5.0 × ULN	> 5.0 – 20.0 × ULN	> 20.0 × ULN
GGT increased	> ULN – 2.5 × ULN	> 2.5 – 5.0 × ULN	> 5.0 – 20.0 × ULN	> 20.0 × ULN
ALP increased	> ULN – 3.0 × ULN	> 3.0 – 5.0 × ULN	> 5.0 – 20.0 × ULN	> 20.0 × ULN
TBL increased	> ULN – 1.5 × ULN	> 1.5 – 3.0 × ULN	> 3.0 – 10.0 × ULN	> 10.0 × ULN
Creatinine increased	> ULN – 1.5 × ULN	> 1.5 – 3.0 × ULN	> 3.0 – 6.0 × ULN	> 6.0 × ULN
CPK increased	> ULN – 2.5 × ULN	> 2.5 – 5.0 × ULN	> 5.0 – 10.0 × ULN	> 10.0 × ULN
Hemoglobin decreased	< LLN – 100.0 g/L	< 100.0 – 80.0 g/L		< 80.0
Neutrophil count decreased	< LLN – 1.5 × 10 ⁹ /L	< 1.5 – 1.0 × 10 ⁹ /L	< 1.0 – 0.5 × 10 ⁹ /L	< 0.5 × 10 ⁹ /L
WBC decreased	< LLN – 3.0 × 10 ⁹ /L	< 3.0 – 2.0 × 10 ⁹ /L	< 2.0 – 1.0 × 10 ⁹ /L	< 1.0 × 10 ⁹ /L
Lymphocyte count decreased	< LLN – 0.8 × 10 ⁹ /L	< 0.8 – 0.5 × 10 ⁹ /L	< 0.5 – 0.2 × 10 ⁹ /L	< 0.2 × 10 ⁹ /L

If there are multiple post-baseline measurements on the same day, the worst value will be used.

Liver Function Tests

Additional summaries will be presented for liver function tests including ALT or serum glutamic-pyruvic transaminase (SGPT), AST or serum glutamic-oxaloacetic transaminase (SGOT), alkaline phosphatase, and total bilirubin. Each laboratory value will be categorized as follows:

- $< 1.5 \times \text{ULN}$
- $\geq 1.5 \times \text{ULN} - < 3.0 \times \text{ULN}$
- $\geq 3.0 \times \text{ULN} - < 5.0 \times \text{ULN}$
- $\geq 5.0 \times \text{ULN} - < 10.0 \times \text{ULN}$
- $\geq 10.0 \times \text{ULN} - < 20.0 \times \text{ULN}$
- $\geq 20.0 \times \text{ULN}$

Shift tables of Baseline to the maximum (relative to the normal range, i.e., the largest multiple relative to the upper limit of normal) values, and from Baseline to final value will be presented using these categories. A listing of potentially clinically important liver function laboratory values will be provided. The listing will include all subjects who met any of the following four criteria:

- $\text{ALT} \geq 3 \times \text{ULN}$, or
- $\text{AST} \geq 3 \times \text{ULN}$, or
- Alkaline phosphatase $\geq 1.5 \times \text{ULN}$, or
- Total bilirubin $\geq 2 \times \text{ULN}$.

A listing of possible Hy's Law cases, defined as those who meet all of the following conditions will be provided:

- $\text{ALT} > 3 \times \text{ULN}$ or $\text{AST} > 3 \times \text{ULN}$
- Associated with an increase in bilirubin $\geq 2 \times \text{ULN}$
- Alkaline phosphatase $< 2 \times \text{ULN}$.

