5.3.3 Safety laboratory parameters

For the visit schedule requiring safety laboratory sampling, see the Flow Charts. The laboratory tests listed in [Table 5.3.3: 1](#) will be performed at the central laboratory service provider. A local laboratory may be used for selected tests in exceptional cases. Patients should be fasting for at least 8 hours prior to the blood sample being taken (except screening visit).

Instructions regarding sample collection, sample handling/ processing and sample shipping are provided in the Laboratory Manual in the ISF.

Laboratory results (i.e. all safety laboratory and clinical laboratory data relevant for current clinical practice of psoriasis patients) of the patients will be available in real time to the respective investigator (via laboratory reports) and to the sponsor (via the central laboratory website) and selected abnormal laboratory alerts will be flagged to the site and sent to sponsor in real time.

Clinically relevant abnormal findings will be reported as baseline conditions or AE's. A clinically relevant value may be either inside or outside the reference range. Clinically relevant abnormal laboratory test results must be confirmed using an unscheduled visit laboratory kit and should be repeated until normalisation or stabilisation or until an alternative explanation has been found. Abnormal laboratory values will be also graded for intensity by using RCTC Version 2.0 criteria ([R13-3515](#)).

Proprietary confidential information © 2016 Boehringer Ingelheim International GmbH or one or more of its affiliated companies
 Table 5.3.3:1 Laboratory tests

Category	Test name
Haematology	Hematocrit (Hct) Hemoglobin (Hb) Glycosylated Hb (HbA1c) Red Blood Cell Count/ Erythrocytes Reticulocyte Count White Blood Cells / Leukocytes Platelet Count/ Thrombocytes
Diff. Automatic	Neutrophils (relative and absolute count) Eosinophils (relative and absolute count) Basophils (relative and absolute count) Monocytes (relative and absolute count) Lymphocytes (relative and absolute count)
Diff. Manual (if Diff Automatic is abnormal)	Neutrophils, bands (Stabs) Neutrophils, polymorphonuclear (PMN) Eosinophils Basophils Monocytes Lymphocytes
Coagulation	Activated Partial Thromboplastin Time (aPTT) Prothrombin time (INR) Fibrinogen
Enzymes	AST(GOT) ALT(GPT) Alkaline Phosphatase (AP) Creatine Kinase (CK) CK-MB, (Only if CK is elevated) Gamma-Glutamyl Transferase (GGT/γ-GT) Lactic Dehydrogenase (LDH) Amylase Lipase

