- If more than one assessment is included in a time window the assessment closest to the nominal day will be used. If there are two observations equidistant to the nominal day, the one after the nominal day will be used in analyses. If more than one assessment is included on the same day, then the worst assessment on that day will be used in analyses, except those specified in Section 11.0.

The protocol specified visits and corresponding time windows used in the efficacy analyses, local tolerability, ECG, laboratory parameters, and vital sign variables, are

presented in the following Table 2, Table 3, Table 4, Table 5, Table 6, Table 7, Table 8, Table 9, Table 10, Table 11, Table 12, Table 13, Table 14, Table 15 and Table 16.

Table 2. Visit Windows for Analysis of PASI, sPGA, Local Tolerability, and Vital Signs in Part A1 (ITT_A1/PP_A1/Safety_A1 Populations)

Window Label	Target Day	Interval
Baseline	1	$\leq 1^a$
Week 4	29	[2, 43]
Week 8	57	[44, 71]
Week 12	85	[72, 99]
Week 16	113	[100, 127 ^b]

Rx Day calculated relative to first dose date of study drug. For subjects randomized but not dosed, Rx Day calculated relative to Randomization.

- a. There is no baseline for local tolerability measurements. If time is collected in vital signs, restrict to records prior to the first dose of study drug.
- b. The minimum of upper bound and first dose date of study drug on or after Week 16 (and within 105 days of last dose for safety analyses). If time is collected in vital signs, restrict to records prior to the first dose of study drug on or after Week 16.

Table 3. Visit Windows for Analysis of DLQI in Part A1 (ITT_A1/PP_A1 Populations)

Window Label	Target Day	Interval
Baseline	1	≤ 1
Week 12	85	[2, 99]
Week 16	113	[100, 127 ^a]

Rx Day calculated relative to first dose date of study drug. For subjects randomized but not dosed, Rx Day calculated relative to Randomization.

- a. The minimum of upper bound and first dose date of study drug on or after Week 16.

Table 4. Visit Windows for Analysis of Safety Laboratory Tests and ECG in Part A1 (Safety_A1 Population)

Window Label	Target Day	Interval
Baseline	1	≤ 1
Week 4	29	[2, 71]
Week 16	113	[72, 155 ^a]

Rx Day calculated relative to first dose date of study drug. For subjects randomized but not dosed, Rx Day calculated relative to Randomization.

a. The minimum of upper bound and first dose date of study drug on or after Week 16 (and within 105 days of last dose for safety analyses).

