11.3 Analysis of Laboratory Data

For the assessments of laboratory data, values observed more than 105 days after the last dose of study drug will be excluded.

Listing and descriptive statistics of laboratory values over time, changes from baseline, and extreme abnormal value on treatment will be provided. Extreme abnormal value is the value which is most significantly away from the reference range. Frequency of subjects with transitions relative to reference range and listing of subjects with significant abnormal laboratory values will be presented as well.

Analyses will be conducted in the Safety_A1 Population, the Safety_B_R Population, and the ALL_RZB Population.

For subjects who were re-randomized to placebo in Part B, laboratory values evaluated after 105 days from the last dose of risankizumab in Part A and before the first dose of retreatment will not be included in the summaries for the ALL_RZB Population.

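### Laboratory shift tables take the minimum and maximum over last-of-day values only, so an earlier, more extreme result on the same day is not counted

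*SAP*

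**What the plan says.** Under Shift Tables, SAP 11.3.2 names three targets: "Shifts from Baseline to the following endpoints will be considered: minimum value, maximum value and final value". The rule for several values on one day follows and makes no distinction between them: "If there are multiple post-baseline measurements on the same day, the last value will be used".

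Other laboratory outputs use different rules:

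- Change from baseline (SAP 11.3.2): "If there are multiple post-baseline measurements on the same day, average value will be used".
- The potentially clinically important and NCI CTCAE part (SAP 11.3.2): "If there are multiple post-baseline measurements on the same day, the worst value will be used". This part includes the high-grade listing: "A separate listing will be provided that presents all of the subjects and values that are NCI CTCAE toxicity grade 3 or above".
- Liver shift tables (SAP 11.3.2, Liver Function Tests): the maximum is the largest multiple of the upper limit of normal (ULN). No same-day rule is given under that heading.
- General convention (SAP 6.0): if several assessments fall on one day, "then the worst assessment on that day will be used in analyses, except those specified in Section 11.0".
- SAP 11.3 also promises an extreme abnormal value: "Extreme abnormal value is the value which is most significantly away from the reference range". It has no last-of-day limit.

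**The concern.** A shift to the maximum is meant to show the highest value a subject reached in the period, and a shift to the minimum the lowest. If only the last value of each day is eligible, the quantity tabulated may be neither. A subject with a high result and a later normal result on the same day appears as normal at maximum unless another day is also high.

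At stake is the count of subjects shifting to low or high in the descriptive safety tables for Safety_A1, Safety_B_R and ALL_RZB. A subject could also appear in the Grade 3 or higher listing and, for the same day and test, as normal at maximum in the shift table. No efficacy result is affected.

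**Working it through.** The plan states no figure to reproduce. The check is on the direction of the effect, on which results are exposed, and on what is known about frequency.

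**Direction.** For one subject and one test, let A be all post-baseline values in the period and L the last value of each day. L is a subset of A, so

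- max(L) ≤ max(A)
- min(L) ≥ min(A)

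The last-value rule can lower a maximum or raise a minimum, never the reverse. A normal value followed by an abnormal one on the same day is counted under either rule, so it offsets nothing.

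**Illustration with assumed values.** ALT: ULN 40 U/L, baseline normal, 220 then 38 U/L on one day, 30 and 33 U/L on two other days.

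| Output in SAP 11.3.2 | Same-day rule | Result |
|---|---|---|
| Change from baseline | average | (220 + 38) / 2 = 129 U/L that day |
| Shift to maximum | last | max(38, 30, 33) = 38; 38 / 40 = 0.95 × ULN; normal to normal |
| CTCAE listing | worst | 220 / 40 = 5.5 × ULN; above 5.0, so Grade 3 in Table 27 |
| Shift to maximum, all values | none needed | max(220, 38, 30, 33) = 220; normal to high |

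Hemoglobin: lower limit 12 g/dL, 7.8 then 12.4 g/dL on one day and 12.9 g/dL on another. Last-value minimum: min(12.4, 12.9) = 12.4, normal. All values: 7.8, low.

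**What is exposed.** In both examples the worst-value rule still captures the subject: 5.5 × ULN exceeds the Table 25 limit of 5.0 × ULN for ALT, and 7.8 is below the Table 26 limit of 8.0 g/dL. Two groups of results lack that protection:

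1. Abnormal values below Grade 3. These do not enter the Grade 3 or higher listing, although the liver listings catch some.
2. Tests in Table 24 with no criteria in Tables 25 to 27. Among the blood tests these are hematocrit, HbA1c, eosinophils, LDH, amylase, lipase, BUN, uric acid, eGFR, CRP, LDL and HDL, twelve in all. Table 26 also has only low limits, so a high white cell or platelet count is not covered.

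**Frequency.** The documents do not give it. As an assumption only, suppose 0.25% to 2% of the 400 subjects planned for risankizumab had, for a given test, an abnormal value hidden by a later same-day normal value and no other abnormal day in that direction. Then 400 × 0.0025 = 1 to 400 × 0.02 = 8 subjects would be misclassified for that test. The documents support neither end of this range, and the true number could be zero.

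**The case against.** The strongest objection is that the rule will seldom bite. Protocol 5.3.3 sends samples to a central laboratory and has abnormal results confirmed with a kit for unscheduled visits. Protocol 6.1 provides additional visits for re-testing, and 6.2.2 lists repeated laboratory testing as a reason for an unscheduled visit. Such repeats will ordinarily fall on a later day, where the first abnormal value stays eligible. This stands, and it limits the size of the point.

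It also defeats a stronger reading. Protocol 5.3.3 says clinically relevant abnormal tests "should be repeated until normalisation or stabilisation or until an alternative explanation has been found", and a reader might infer that the last same-day value is systematically nearer normal. The text describes repeats over time and does not say that they occur on one day. Nor do the documents show that same-day pairs cluster in acute work-ups. The unscheduled blood test in Protocol 5.3.6.1 is for symptoms where no liver results are available, so it is a first sample.

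A second objection is that SAP 6.0 permits exceptions in Section 11.0, so different same-day rules for different outputs are allowed. This also stands: a reader might infer that the SAP contradicts itself, and it does not. But permission is not a reason, and the SAP gives none for using the last value for an extreme.

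A third objection is that serious signals are caught elsewhere. The Grade 3 or higher listing shows the whole course of the parameter, liver tests have their own listings, including possible Hy's Law cases, and clinically relevant findings are reported as adverse events. This is largely right. It leaves the lower-grade shifts and the tests without criteria.

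**Conclusion.** The point holds as a minor defect of analysis choice. As written, the shifts to minimum and maximum are computed over last-of-day values. Against an all-values rule this can only undercount shifts to low or high. It does so when the more extreme value came earlier on a day with several values and no other day is abnormal in that direction.

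The size is unknown and probably small, since it depends on a count of same-day repeats that the documents do not give. Modelling how often a repeat falls back into range would not settle this: the answer would depend on an assumed correlation and would apply only to days that have a same-day pair.

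The tables could disagree about a subject's day, with Grade 3 in the listing and normal at maximum in the shift table. A reader might take this as one sample classified in two ways. It is not: it needs two different samples on the same day.

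Whether the liver shift to the maximum already uses the worst same-day value is also an inference. It would come from the convention in SAP 6.0, which sits within the visit-window algorithm; the liver text itself is silent.

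**What to change.** In SAP 11.3.2, Shift Tables:

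- Limit the last-value rule to the shift to the final value.
- For the shift to the minimum, use the lowest post-baseline value in the analysis period; for the shift to the maximum, use the highest. Include every value on days with more than one, within the existing 105-day limit of SAP 11.3.
- Under Liver Function Tests, state that the highest value also applies to the shift to the maximum.

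This costs a sentence or two of SAP text and a small programming change. It needs no new data and changes no efficacy analysis and no entry in the Grade 3 or higher listing.

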11.4 Analysis of Vital Signs and Weight

Analyses will be conducted in the Safety_A1 Population, the Safety_B_R Population, and the ALL_RZB Population.

For subjects who were re-randomized to placebo in Part B, vital sign values evaluated after 105 days from the last dose of risankizumab in Part A and before the first dose of retreatment will not be included in the summaries for the ALL_RZB Population.

11.4.1 Variables and Criteria Defining Abnormality

The following vital sign parameters will be assessed: Systolic blood pressure [mmHg], Diastolic blood pressure [mmHg], Pulse [beats per minute], Respiratory rate [breaths per minute], Temperature [°C], Weight [kg]. The following table presents the Criteria for Potentially Clinically Important Vital Sign Findings. Of note, a post baseline value must be more extreme than the baseline value to be considered a potentially clinically important finding.

Table 28. Criteria for Potentially Clinically Important Vital Sign Findings

Vital Sign	Category	Criteria for Potential Clinically Important Vital Signs
Systolic Blood Pressure	Low Value	≤ 90 mmHg and decrease ≥ 20 mmHg from Baseline
	High Value	≥ 160 mmHg and increase ≥ 20 mmHg from Baseline
Diastolic Blood Pressure	Low Value	≤ 50 mmHg and decrease ≥ 15 mmHg from Baseline
	High Value	≥ 105 mmHg and increase ≥ 15 mmHg from Baseline
Pulse	Low Value	≤ 50 bpm and decrease ≥ 15 bpm from Baseline
	High Value	≥ 120 bpm and increase ≥ 15 bpm from Baseline

Note: A post baseline value must be more extreme than the baseline value to be considered a potentially clinically important finding.

11.4.2 Statistical Methods

Changes from Baseline to each visit and to the final value in vital sign parameters will be summarized with the mean, standard deviation and median. The Baseline and final value means will also be presented for subjects who have both the Baseline and final values (see Section 6.0 for the definition of Baseline and final values).

For baseline, if there are multiple measurements on the same day, the last measurement prior to the first dose of study drug will be used as the Baseline vital sign value. If there are multiple post-baseline measurements on the same day, average value will be used.

For systolic blood pressure, diastolic blood pressure and pulse, a listing of all subjects with any vital sign value meeting criteria for potentially clinically important values will be provided. For each of these subjects, the whole course of the respective parameter will be listed. The number and percentage of subjects who have at least one value meeting criteria for potentially clinically important values will be provided for each selected vital sign parameter.

